5.3. Vital Signs, Physical Examination Findings and Electrocardiogram (ECG)

Similar to laboratory tests, only vital signs abnormalities emerging after vaccination will be tabulated by worst abnormality grade. a

Heart rate (beats per minutes, bpm), respiratory rate (breaths per minute), systolic blood pressure (mmHg) and diastolic blood pressure (mmHg) will be collected. The respective vital signs abnormalities are defined in Table 5. Moreover, only the vital signs values will be used, no clinical interpretations, therefore, grade 3 and 4 is shown combined as grade 4 always requires clinical interpretation.

Table 5: Vital Signs Toxicity

Vital Signs	Grade 1	Grade 2	Grade 3 /4
Tachycardia – beats (HR) per minute	101 – 115	116 – 130	>130
Bradycardia – beats (HR) per minute	50 – 54	45 – 49	< 45
Hypertension (systolic) - mm Hg	141 – 150	151 – 160	>160
Hypertension (diastolic) - mm Hg	91 – 95	96 – 100	>100
Hypotension (systolic) - mm Hg	85 – 89	80 – 84	< 80
Respiratory Rate - breaths per minute	17-20	21-25	>25

Temperature from diary, on-site assessments from day of vaccination and any on-site assessment performed between the vaccination visit and the visit 7 days post-vaccination (from 37.5° C until 40°C, in steps of half degree increments, e.g., <37.5, 37.5-<38, 38-<38.5, ... >40). A table will be created, showing the maximum temperature for both diary and onsite assessments combined.

Any abnormal physical examination result will be documented as AEs, by the investigator. For Cohorts 1 and 2, any abnormalities in ECG parameter (at screening) will be listed.

5.4. Respiratory Tract Infection (RTI) Forms

During the RSV season(s), participants should record any signs and symptoms of RTI (such as runny nose, fever, severe cough, rapid breathing, difficulty breathing), including measurement of body temperature, on a daily basis until symptoms have resolved using a specific RTI Symptoms Form.

The number of subjects with confirmed RSV infections (based on RT-PCR results or a serological assay) will be summarized per period and per group in case enough cases revealed, otherwise these data will be listed.

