^a The second RSV season of the study is defined relative to the enrollment date of the first participant in Cohort 1.

Hypothesis

No formal statistical testing of safety and immunogenicity data is planned. Data will be analyzed descriptively.

OVERVIEW OF STUDY DESIGN

This is a multi-center, randomized, double-blind, placebo-controlled Phase 1/2a study for safety and immunogenicity evaluations for regimen selection of Ad26.RSV.preF and RSV preF protein combinations followed by expanded safety evaluation of the selected regimen in male and female participants aged ≥ 60 years who are in stable health.

To further extend the assessment of the long-term durability of the immune response to the study vaccine, participants in Groups 14 and 15 (Cohort 2) will continue into a long-term follow-up phase.

The study design includes 3 sequential cohorts: an initial safety cohort (Cohort 1 in a total of 64 participants), a regimen selection cohort (Cohort 2 in a total of 288 participants), and an expanded safety cohort (Cohort 3 in a total of 315 participants).

The overall total number of participants will be approximately 667.

The study duration will be approximately 730 days (2 years) per participant in Cohorts 1 and 2 (Groups 11-13 and Groups 16-18), and approximately 1095 days (3 years) per participant in Cohort 2 (Groups 14-15) and Cohort 3. The study comprises a maximum 28-day screening period for Cohorts 1 and 2 (screening for Cohort 3 will be performed pre-vaccination on Day 1), study vaccination (active or placebo) with a one-dose (on Day 1) or two-dose (on Day 1 and Day 57) regimen and a booster dose (active or placebo) at Month 12 (Cohort 1) or at Month 12 and Month 24 (Cohort 3), a minimum 28-day follow-up period after each vaccination, and a follow-up period until 2 years after the first Ad26.RSV.preF or RSV preF protein vaccination (Cohorts 1 and 2 [Groups 11-13 and Groups 16-18]) or until 3 years after the first Ad26.RSV.preF or RSV preF protein vaccination (Cohort 2 [Groups 14-15] and Cohort 3). The end of the study is defined as the last participant's last visit 24 months after the first vaccination (Cohorts 1 and 2 [Groups 11-13 and Groups 16-18]) or the last participant's last visit approximately 1095 days (3 years) after the first vaccination (Cohort 2 [Groups 14-15] and Cohort 3).

An internal data review committee (DRC) will be established for this study to evaluate safety and reactogenicity data on a regular basis.

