
 • To assess the long-term durability of the immune response in groups receiving a booster at different time intervals 	
 • Assays to be used include, but are not limited to, RSV neutralizing antibody levels against A and B strain, RSV F protein binding antibodies (ELISA; pre-F and/or post-F), RSV F protein specific functional antibodies, and RSV F protein specific IFN-γ ELISpot at Days 758, 912 and 1095

 • To evaluate symptoms of respiratory illness (including respiratory illness due to RSV) via the RTI Symptoms Form 	
 • During the RSV season: Signs and symptoms of RTI (including RTI due to RSV) from Day 1 until the end of the second RSV season of the study^a

 • Characterization of viral or bacterial infections in the respiratory tract 	
 • Assessment, typing and level of infection by RT-PCR or response to respiratory infection by serology

See Section 9.2 for evaluations related to endpoints.

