The **26-week post-vaccination visits** include an abbreviated physical examination and vital signs measurement (both at the discretion of the investigator) and recording of any SAEs and associated concomitant medications, and RTIs.^a Blood samples for immunogenicity assessments will be collected.

^a RTIs will only be recorded during the first 2 RSV seasons of the study (relative to the enrollment date of the first participant in Cohort 1).

^b Visit 13 (7 days post-third vaccination) is not required for any Cohort 3 participant who misses the third vaccination.

The **12-month post-first vaccination visit** includes an abbreviated physical examination and vital signs measurement (both at the discretion of the investigator) and recording of any SAEs and associated concomitant medications, and RTIs.^a Blood and nasal samples for immunogenicity assessments will be collected.

The **18-month post-first vaccination visit** (Cohort 2 only) includes an abbreviated physical examination and vital signs measurement (both at the discretion of the investigator) and recording of any SAEs and associated concomitant medications, and RTIs.^a Blood samples for immunogenicity assessments will be collected.

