Regimen	2	Post-Boost (Month 24)	4	Date and time of Month 24 Boost	Minimum of: a) 23:59 at the date of database cut-off b) Maximum (28 days after the Month 24 boost vaccination at 23.59, scheduled visit 4 weeks after the Month 24 boost vaccination at 23:59) c) 23:59 at the date of last contact (for completed and early discontinuation of the study)

Table 1: Phase Definitions of Cohort 1, 2 and 3

Phase	Phase number	Period	Period number	Interval	
				From	To
Follow-Up Boost (Month 24)	6			1 minute after end of Post-Boost (Month 24) period	Minimum of: a) 23:59 at the date of database cut-off b) 23:59 at the date of last contact (for completed and early discontinuation of the study)

^a in case an earlier date is available (eg. for lab or vital signs), then use the very first date to include all data

In case the one-dose regimen is selected (Groups 11 through 16 from Cohort 2) after the evaluation of Cohort 2, then the post dose 2 and follow up 2 will not be applicable.

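### SAP 5.4 counts confirmed RSV infections by dosing period but does not limit the count to the two seasons of RTI surveillance, so Cohort 3 counts are not comparable across periods

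*SAP*

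**What the plan says.** **SAP.** Section 5.4 plans a single count of RSV infections, confirmed by RT-PCR or by serology: "The number of subjects with confirmed RSV infections (based on RT-PCR results or a serological assay) will be summarized per period and per group". The same sentence makes the table conditional; the count "will be summarized per period and per group in case enough cases revealed, otherwise these data will be listed". What counts as enough is not defined. On timing, the section says only: "During the RSV season(s), participants should record any signs and symptoms of RTI". It does not mention two seasons.

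Phases and periods are defined in SAP 2.1.1, Table 1, from the date and time of each dose. The last active one starts at "Date and time of Month 24 Boost" and is followed by a Month 24 follow-up phase.

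SAP 6.1.1.1 separately treats a 4-fold rise in Ga or Gb ELISA as infection and summarises those participants per period and regimen, with no season limit.

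**Protocol.** Section 9.1.6 (footnote) says: "RTIs will only be recorded during the first 2 RSV seasons of the study". The Schedule of Activities and Section 9.2.2 put the same limit on symptom forms, home swab kits and the 30-day telephone calls. The anchor is shared by all cohorts: "The second RSV season of the study is defined relative to the enrollment date of the first participant in Cohort 1". The exploratory endpoint has the same end: "Signs and symptoms of RTI (including RTI due to RSV) from Day 1 until the end of the second RSV season of the study". The Cohort 3 final visit at Month 36 (Section 9.1.7) does not include RTI recording, whereas the Month 24 final visit of Cohorts 1 and 2 does.

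**The concern.** The table is organised by dose, while the ascertainment is organised by calendar season. Where the two separate, a period with forms, swab kits and calls stands beside a period without them, and nothing in SAP 5.4 tells the reader which is which.

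This matters most in Cohort 3. Its objective includes deciding whether a booster is needed at Month 12 and/or Month 24. A count that falls from the post-dose-1 periods to the Month 24 periods invites the reading that revaccination prevented RSV, when the change in surveillance alone could produce the fall.

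Adding RT-PCR and serology together compounds this. RT-PCR detection depends largely on the surveilled seasons. Serology can use any immunogenicity blood sample to the end of the study. The mix of the two therefore changes from period to period.

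**Working it through.** The plan has no figure of its own to reproduce. The question is whether the second RSV season can still be running at the Cohort 3 boosters. The documents give neither the first enrolment date nor season dates, so bounds and ranges are shown.

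**1. Earliest Cohort 3 Month 24 dose, in days after the first Cohort 1 dose.**
- Cohort 1 needs four consecutive 7-day reviews (R1a to R1d): 4 × 7 = 28 days.
- The Cohort 2 primary analysis needs Day 85 safety data: 84 days. Sum: 28 + 84 = 112. Enrolment, assay and decision time are taken as zero.
- The Month 24 dose is Vac 1 + 729 days, window ±30 days: 112 + 729 − 30 = **811 days**.

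**2. Latest end of the second season.**
- If a season in progress at first enrolment counts as the first, or none is in progress, the first season ends within one year and the second within two, at most 731 days. As 811 > 731, no Month 24 time is surveilled, whatever the calendar or hemisphere.
- If a season in progress is not counted, the second can end later. With an assumed September–April season and first enrolment on 2 September 2018, it ends on 30 April 2021, 971 days later. With November–March and enrolment on 2 November 2018, it ends 880 days later.
- Overlap then needs Cohort 3 to open within 112 + (971 − 811) = 272 days of the first Cohort 1 dose, or 112 + (880 − 811) = 181 days.

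**3. Range over assumed dates.** First Cohort 1 dose on 15 February, 1 May, 1 July, 1 September or 1 November 2018; season October–March, September–April or November–March; season in progress counted or not; Cohort 3 opening 112, 180, 270 or 365 days later.

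| Interval | Second-season days inside it |
|---|---|
| Cohort 1 after Month 12 | 30 to 243 |
| Cohort 3 after Month 12 | 0 to 243 |
| Cohort 3 after Month 24 | 0, except 3 to 101 with a 1 November start, season in progress not counted, and Cohort 3 opening by 180 days |

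Between these start dates the exception can be longer but needs the same conditions. The extreme is a 2 September 2018 start: 2 September 2018 + 811 days = 21 November 2020, and from then to 30 April 2021 is 161 days.

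*One example.* First dose 1 July 2018, October–March season, Cohort 3 opening 180 days later. The second season ends on 31 March 2020. The first Cohort 3 Month 12 dose (Day 365) falls on 27 December 2019, leaving 96 surveilled days (5 + 31 + 29 + 31). The earliest Month 24 dose falls on 26 November 2020, 240 days after surveillance ended.

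Protocol Amendment 6, dated 6 November 2020, was still changing the Group 20 Month 24 dose. This fits Month 24 dosing lying ahead at that date.

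**4. What remains after the second season.** RT-PCR can still come from scheduled nasal samples (Cohort 3 Days 730 and 758, usable for etiology if needed), from RTIs meeting SAE criteria at any time, and from RTIs recorded as AEs within 28 days of a dose. Serology can use the blood drawn at Days 730, 744, 758, 912 and 1095.

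**5. Denominator.** SAP 5 divides by subjects with considered data in the period. This helps only if unsurveilled time is declared not considered, and SAP 5.4 does not declare it. SAP 5.1.4, in the adverse event section, treats non-reporters as without an event. Carried over to 5.4, that rule would turn absent surveillance into absent infection.

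**6. Meaning of period.** Table 1 numbers only the post-dose intervals of about 28 days as periods; follow-up rows are phases, though SAP 5.1.3 calls them non-active periods. The mismatch holds under either reading.

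**The case against.** The case against is substantial. The table is conditional, and a listing has no denominators or zeros. The endpoint is exploratory, is defined by the protocol to end with the second season, and carries no formal test. SAP 1.1 defers to the protocol for objectives, and the SAP's loose season wording does not contradict two seasons. Placebo Group 21 loses surveillance at the same time as Groups 19 and 20, so its count would fall too and warn a careful reader.

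All of that lowers the stakes, but it does not remove the gap. Cases from monitored periods can be enough to trigger the table, which then prints monitored and unmonitored time side by side. A listing does not show where surveillance stopped either. The concurrent placebo group protects comparisons between groups within a period, not comparisons across periods.

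A reader might infer two stronger things:
- **That RT-PCR counts after the boosters are zero by design.** They are not. The incidental routes in step 4 remain open, and SAP 5.4 plans no RT-PCR-only cell, only a count that includes serology.
- **That every post-booster period is affected.** On the dates tried, Cohort 1 has 30 to 243 second-season days after its Month 12 booster, fewer if the first enrolment fell right at a season boundary. Cohort 3 Month 12 cannot be settled without enrolment dates. Only Cohort 3 Month 24 supports a firm statement.

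**Conclusion.** The point holds for Cohort 3. Active RTI swabbing will almost certainly have ended before the Month 24 dose; the exception needs a first enrolment during a season that was not counted and a fast opening of Cohort 3. It may also have ended before or during the Month 12 follow-up (0 to 243 surveilled days, depending on dates not given). RT-PCR ascertainment after that is reduced and uneven, so counts cannot be compared across periods, and a fall after Month 24 is not evidence of a booster effect.

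The number of infections missed cannot be estimated from the documents. A reader might apply the 5% to 10% yearly infection rate in Protocol 1.1 to the 270 participants in Groups 19 and 20. That rate refers to residents of long-term care facilities, while this trial enrols people in good or stable health, and attrition by Month 24 is unknown.

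This is an inexpensive improvement to a descriptive, exploratory summary. It does not affect the primary safety or immunogenicity analyses.

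**What to change.** Revise SAP 5.4 as follows.

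- State the protocol's two-season limit, and say whether a season in progress at the first Cohort 1 enrolment counts as the first.
- Summarise RT-PCR-confirmed RSV by surveilled season and group, with participants under surveillance in that season as denominator. A split by last dose received before onset is optional.
- Label periods after the second season 'no active surveillance' instead of printing a count over the full group, and list any incidental RT-PCR positives there.
- Report serology-based infections in a separate table with the number tested as denominator, using the definition in SAP 6.1.1.1 so that the same cases are not tabulated under two rules.
- Keep the listing as the fallback for few cases, with a column showing whether onset fell within surveilled time.

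The cost is SAP wording and a changed table shell, with no new data collection. The drawback is that there will be no per-period RT-PCR rate for Month 24, which the design cannot supply in any case.

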6. IMMUNOGENICITY ANALYSIS

The analysis of all secondary and exploratory immunogenicity endpoints related to RSV will be based on the PPI set.

6.1. Secondary and Exploratory Endpoints

The following humoral and cellular immune responses will be measured as part of the evaluation of secondary and exploratory objectives for both cohorts:

Immunogenicity against the insert:

Humoral immune response

- RSV A2 neutralizing titers of the vaccine-induced immune response
- Antibodies binding to RSV F protein in post-fusion (Post F) and pre-fusion (Pre F) form (RSV F-protein enzyme-linked immunosorbent assay [ELISA])

In addition, exploratory analyses may be performed to further investigate vaccine-elicited immune responses. These may include, but are not limited to, the following:

- RSV cross-neutralization of B strain
- Intranasal pre-F and Post-F antibody, from nasal wash samples
- Fc receptor function assays

Moreover, additional humoral immune responses may also be measured as part of further evaluation of exploratory objectives for both cohorts:

Humoral immune response

- RSV cross-neutralization of other A strain

Cell-mediated immune response

- ELISpot IFN γ assay (units: SFU/10⁶ PBMC). An ELISpot assay is used to quantify the amount of peripheral blood mononuclear cells (PBMCs) able to produce IFN γ upon RSV F-protein peptide stimulation.
- Intracellular cytokine staining (ICS, unit: % of subset) or cytokine analysis. Analysis of CD4 and CD8 T-cell subsets and their cytokine expression patterns will be determined by flow cytometry after RSV F-protein peptide stimulation (including, but not limited to CD4/CD8, interleukin-2 [IL-2], IFN γ , TNF α and Th1/Th2 subtyping).

Moreover, additional cellular immune responses may also be measured as part of further evaluation of exploratory objectives for both cohorts:

- Cytokine analysis, Cytokine profiles of (in vitro) stimulated PBMC supernatant will be analysed to assess the quantity and quality of the elicited immune responses, including

Th1/Th2 balance. Analysis will include, but is not limited to, IFN γ , IL-2, IL-4, IL-5, IL-13, TNF α , CD107a, Granzyme B, and CD154, if available.

- Sequencing of B-cells
- Transcriptome analysis

Immunogenicity against the vector:

- Adenovirus neutralization assay

This assay assesses neutralizing antibody responses against the Ad26 vector.

Immunogenicity to assess RSV exposure

- N protein antibodies (ELISA)
- Ga and Gb protein antibodies (ELISA)

6.1.1. Secondary and Exploratory Immunogenicity Analysis

No formal hypothesis on the secondary and exploratory immunogenicity parameters will be tested.

6.1.1.1. Humoral Assays

For VNA and ELISA assays following results will be calculated: N, geometric mean[§] and corresponding 95% CI of the actual values and fold increases from baseline will be tabulated and graphically presented. *§calculate the mean and corresponding 95%CI of the log₂ transformed values, back-transform this mean [i.e. 2^{mean}] and CI [i.e. 2^{CI}].*

Actual values and fold changes from baseline are tabulated and shown as dot plots with dots for subject values, and the corresponding geometric mean and 95% CI per time point for each assay. In addition, GMT plots over time, combining the regimens in one graph (without individual subject dots) will also be created.

Ratios of actual values and of fold changes from baseline between humoral assays may also be presented.

Subject profiles of the actual values over time will be graphically presented.

Reverse distribution curves of the actual values are provided for selected time points.

In the graphs, original values will be displayed on the log₂ scale.

Scatterplots between humoral assays may be provided for the most important time points. In these scatterplots the actual values will be shown, even if they are below the LLOQ, but the LLOQ cut-off will be visualized in the graph per assay if some values are below LLOQ.

Moreover, subjects with a 4-fold increase in Ga or Gb ELISA will be considered as infected and the number of infected subjects will be summarized per period and regimen. The subject profiles of the assays against the insert will also be repeated, highlighting the infected infected subjects based on Ga or Gb ELISA

Other exploratory parameters may be analysed at the discretion of the sponsor.

6.1.1.2. Cellular Assays

For **ELISpot**, following results will be calculated: N, median, quartiles, minimum and maximum of the actual values will be tabulated and graphically presented.

Subject profiles of the actual values over time will be graphically presented.

Actual values are shown as box plots with dots for subject values, and the corresponding median and interquartile range per time point for each assay. In addition, box plots over time, combining the regimens in one graph (without individual subject dots) will also be created. For the graphs, original values will be displayed on the \log_{10} scale.

For **ICS** and **PBMC secreted** cytokines, if available, analyses may include:

Total Cytokine response: the % of subsets expressing at least IFN γ , TNF α or IL2 will be calculated for CD4 and CD8, separately.

For total cytokine responses, tables with number of observations, median, first and third interquartile per timepoint will be provided.

Subject profiles of the actual values over time will be graphically presented.

Actual values are shown as box plots with dots for subject values, and the corresponding median and the first and third quartile (Q1, Q3) per time point.

For cytokine combinations (for example, IFN γ and/or TNF α and/or IL2), bar charts reflecting the median magnitude of each combination may be graphically presented. In that case, tables with the corresponding descriptive statistics will also be provided.

Th1 and Th2:

Th1 is defined as %RSV-F specific CD4 T-cells IFN γ + AND/OR IL2+.

Th2 is defined as %RSV-F specific CD4 T-cells IL4+ AND/OR IL13+ AND CD40L+.

Subject profiles and graphs of the actual values over time (box-plot type) will be created. In addition, at time points of interest, scatterplots of Th1 vs Th2 might be created. For the graphs, original values will be displayed on the \log_{10} scale.

Scatterplot with humoral and cellular assays may be provided for the most important time points.

The technical details for the calculation of the ICS values to be used in the graphs will be outlined in the data presentation specifications (DPS) document.

